Title of the Study: CONTINUOS SUBCUTANEOUS INSULIN INFUSION IN ITALY (IMITA2)

Date: 30th March 2015

NCT02620917

Study Design

In this multicentre cross-sectional study, data were collected using questionnaires sent by e-mail to adult and paediatric diabetes care centres that use CSII (continuous subcutaneous insulin infusion) for treatment. Centres were identified from previous surveys and through information from companies selling CSII devices. Incomplete data were obtained by phone or e-mail and integrated. Subjects treated with CSII for at least 1 year were consecutively enrolled among people who attended diabetes outpatient clinics between September 2015 and October 2016. Exclusion criteria were previous diagnosis of dementia or psychosis and pregnancy in progress. Before enrolment, informed consent was obtained from each participant. The study was approved by the ethical committee of each centre. Procedures complied with the ethical standards of the institutional and national committees on human experimentation and with the Helsinki Declaration of 1975.

Information on standard clinical variables (i.e. serum HbA1c, total cholesterol, high-density lipoprotein [HDL] cholesterol, triglycerides and creatinine), demographic data (i.e. age, gender, type of diabetes, duration of diabetes, duration of treatment with CSII and body mass index) and presence of hypertension and chronic diabetic complications (i.e. retinopathy, nephropathy and vasculopathy [cerebral, cardiac and peripheral]) was derived from local clinical management systems. The median HbA1c level of participants from the year before the study was calculated. Information on pump characteristics, use of advanced pump functions (i.e. different bolus types, bolus calculator and temporary basal rates), days of sensor use and frequency of self-monitoring of blood glucose was obtained from insulin pumps or glucometers or recovered from CGM receivers and was reported in the questionnaire.

Participants were asked to record the number of severe hypoglycemia episodes (SH) experienced during the year preceding enrolment in the study, and the frequency of episodes was expressed as the cumulative number of SH episodes per participant. For adult participants, an SH episode was defined as an event requiring assistance and the administration of carbohydrates (CHOs) or glucagon. For paediatric participants, the SH episode referred to an event associated with coma, seizures or neurological symptoms requiring parenteral treatment. The number of diabetic ketoacidosis (DKA), defined as acidosis and hyperglycaemia, and the number of visits to the emergency room for acute metabolic complications of diabetes were collected from medical records. Information about the organisation of each centre included the number of people with T1DM, start of CSII treatment, team composition (physicians, nurses, dieticians and psychologists) and around-the-clock availability.

Statistical analysis

Continuous data were expressed as median and interquartile range (IQR). Categorical data were compared

between groups using the chi-square test, whereas continuous data were compared between groups using the ManneWhitney or KruskaleWallis test. All tests were two sided, and a p value less than 0.05 was considered to be significant. A linear mixed-effect regression model was used to identify the predictors of HbA1c among clinically relevant variables (i.e. age, duration of diabetes, duration of CSII treatment, type of device, use of sensor-based treatment, CHO counting and use of advanced pump functions) that account for the centre's effects. The centre was included in the model as a random effect because participant outcomes were expected to differ from centre to centre, possibly owing to differences among centres instead of differences among participants who present at different centres. Statistical analysis was performed using R 3.3.2 (The R Foundation for Statistical Computing, Vienna, Austria)

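### Severe hypoglycaemia is defined more broadly in adults than in children; if the plan's unstratified tests are applied to it across both age groups, the result partly reflects the definition

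*Combined protocol and SAP*

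**What the plan says.** The combined protocol and SAP describes a survey based on "questionnaires sent by e-mail to adult and paediatric diabetes care centres", so both age groups are in the sample. The Study Design section defines SH twice. For adults, "an SH episode was defined as an event requiring assistance and the administration of carbohydrates (CHOs) or glucagon". The next sentence sets the paediatric rule: "For paediatric participants, the SH episode referred to an event associated with coma, seizures or neurological symptoms requiring parenteral treatment". It gives no age or centre rule for deciding which definition a participant received.

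Both definitions lead to the same measure, reported by participants for the year before enrolment: "the frequency of episodes was expressed as the cumulative number of SH episodes per participant".

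Under Statistical analysis, continuous data are summarised by median and interquartile range. Categorical data are compared "between groups using the chi-square test, whereas continuous data were compared between groups using the ManneWhitney or KruskaleWallis test". The groups are not defined, and no stratification or separate analysis by age group is stated. The one adjusted analysis concerns another outcome: "A linear mixed-effect regression model was used to identify the predictors of HbA1c". Age is among its candidate predictors and centre is a random effect.

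**The concern.** An assisted episode treated with oral carbohydrate, without coma, seizure or neurological symptoms, counts in an adult and not in a child. At the same true risk, a child therefore tends to record fewer SH episodes than an adult. Where a group contains more children, its SH count falls for that reason alone. An unstratified test cannot separate this from an effect of device or sensor: it may report a difference that is not there, or hide one that is. Age adjustment in the HbA1c model does nothing for SH.

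Age-specific definitions may well be deliberate, and nothing here asks for either to change. The issue is that the analysis text does not carry the distinction through.

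**Working it through.** **1. Do the definitions differ in a way that matters?** The phrase about parenteral treatment could qualify all three paediatric features or only the last. On either reading, an orally treated assisted episode without those features is excluded in a child and included in an adult. The definitions are not strictly nested: on the second reading, a child's seizure without such treatment would count, while an adult's seizure without assistance and carbohydrate or glucagon would not.

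**2. Is there a stated figure to reproduce?** No. The documents give no SH rate, age mix, group size or power. They give only the two-sided 5% level. Everything below is illustration under assumptions.

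**3. Assumptions.** The adult-definition rate is 0.2 per year, with equal true risk in children and adults. A share f of adult-definition episodes also meets the paediatric definition, with f = 0.1, 0.3, 0.5 or 0.7. Counts are Poisson unless stated. A single f treats paediatric events as a subset of adult ones, which simplifies step 1.

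**4. Effect on summaries.** With shares of children a and b in two groups, the ratio of mean counts is [(1−a) + a·f] / [(1−b) + b·f]. For a = 0.4 and b = 0.2:
- f = 0.1: 0.64/0.82 = 0.78
- f = 0.3: 0.72/0.86 = 0.84
- f = 0.5: 0.80/0.90 = 0.89
- f = 0.7: 0.88/0.94 = 0.94

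With a = b the ratio is 1.00.

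The probability of any episode is 1 − exp(−0.2) = 18.1% in adults. In children it is 1 − exp(−0.2f), which is 2.0% at f = 0.1 and 13.1% at f = 0.7. At f = 0.1, the proportion with any episode is 0.6 × 18.1% + 0.4 × 2.0% = 11.7% in the first group and 0.8 × 18.1% + 0.2 × 2.0% = 14.9% in the second. Since fewer than 25% have an episode in every group, the median (IQR) is 0 (0 to 0) throughout and shows no distortion.

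**5. Effect on tests.** Simulation used 4,000 runs per cell (simulation standard error at most 0.8 points), a tie-corrected Mann-Whitney test, and the van Elteren test stratified by definition. Entries are % rejecting at two-sided 5%.

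| Setting (share of children in each group) | f = 0.1 | 0.3 | 0.5 | 0.7 |
|---|---|---|---|---|
| *No true difference* | | | | |
| Mann-Whitney, 500 per group, 40% vs 20% | 33.7 | 20.3 | 12.3 | 7.1 |
| Same, overdispersed (negative binomial, size 0.5) | 25.5 | 14.6 | 9.2 | 6.8 |
| Mann-Whitney, 200 per group, 40% vs 20% | 15.1 | 10.6 | 8.3 | 5.7 |
| Mann-Whitney, 500 per group, 30% vs 20% | 10.6 | 7.7 | 6.8 | 6.0 |
| Mann-Whitney, 500 per group, 30% vs 30% | 4.4 | 5.1 | 4.9 | 4.7 |
| van Elteren, 500 per group, 40% vs 20% | 5.0 | 4.9 | 5.3 | 5.1 |
| 300 children vs 700 adults, Mann-Whitney | 100 | 100 | 95.6 | 52.7 |
| 120 children vs 280 adults, Mann-Whitney | 100 | 94.1 | 61.3 | 24.0 |
| *True rate ratio 0.6, 500 per group (power)* | | | | |
| Mann-Whitney, 20% vs 40% | 23.7 | 41.5 | 57.1 | 73.0 |
| van Elteren, 20% vs 40% | 74.4 | 77.8 | 80.0 | 83.6 |
| Mann-Whitney, 30% vs 30% | 74.9 | 78.2 | 81.0 | 84.4 |
| van Elteren, 30% vs 30% | 76.3 | 79.3 | 81.5 | 84.6 |

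Repeat runs of the first cell gave about 32%, so it is quoted as about 33%. The masking rows follow from step 4: when the lower-risk group has 20% children and the other 40%, a true ratio of 0.6 appears as 0.6/0.78 = 0.77 at f = 0.1.

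**6. Limit of the stratified test.** The results above assume independent participants, but the plan itself expects outcomes to differ between centres. If SH rates vary by centre (assumed coefficient of variation 0.5, 20 centres per stratum in each group, groups drawn from different centres), van Elteren rejects in 12% to 13% of null runs. That excess comes from clustering, not from the definition.

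**The case against.** The strongest reply is that the error is read out of silence. The plan names no SH comparison and does not say that adults and children are pooled. Its undefined groups are compatible with separate adult and paediatric analyses. This stands, and it is why the point is conditional: a reader might infer that an unstratified SH test across ages is planned, and the documents do not say so. They do collect SH, express it per participant, and offer only generic tests, with nothing to prevent that use.

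A reader might also infer that every SH summary is distorted. That is not supported: under the assumptions above the stated median and IQR show nothing. Only a pooled mean, a proportion with any episode, or a test would.

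The sizes are wholly assumed, and the large ones need low f, a marked imbalance in the share of children and large groups. With overdispersion, smaller groups or closer shares they shrink, and at high f they are close to nominal. This also stands.

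Finally, an unadjusted child-versus-adult contrast would be hard to interpret even with one definition, because age affects much else. True, but the definition adds a built-in difference that no later adjustment for age could separate from risk.

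**Conclusion.** The point holds in conditional form. The two definitions differ materially, they feed one count, and the stated tests ignore which one applied. If SH is compared across both age groups with those tests, a child-versus-adult contrast always mixes definition with risk. A device or sensor contrast does so only when the groups have unequal shares of children.

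The documents do not allow the size to be derived. Under Poisson counts at 0.2 per year, equal true risk, 500 per group and 40% versus 20% children, the false-positive rate runs from about 33% (f = 0.1) through about 12% (f = 0.5) to about 6–7% (f = 0.7). With equal shares it is nominal.

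HbA1c, and SH comparisons within one definition, are unaffected. The study's HbA1c model is not called into question. This is a correction worth making to a safety outcome, and it has a cheap remedy.

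**What to change.** - State the rule that decided which definition each participant received (age cut-off or centre type) and hold the result as a variable.
- Report SH separately by definition applied.
- Make any SH comparison within definition, or with a test stratified by it: van Elteren for counts, Cochran-Mantel-Haenszel for any episode yes/no.
- Make no direct adult-versus-child SH comparison unless episodes can be classified to one common definition from data already held. The plan describes only the number of episodes being recorded, so this may not be possible.

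The cost is SAP wording, a split of existing tables and one stratified test. Age and centre are already available. If neither rule was fixed, centres would have to be asked, by the phone or e-mail follow-up already used for incomplete data.

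There are three downsides. Separate paediatric figures will be imprecise: in the 500-per-group example with 40% versus 20% children, the expected events are 200 × 0.2 × f versus 100 × 0.2 × f, that is 4 versus 2 at f = 0.1 and 20 versus 10 at f = 0.5. The stratified combined test limits that loss (with 30% children in both groups and f = 0.1, power is 76% against 75% unstratified), but this assumes the same rate ratio in both strata, and it works best when the effect has the same direction in both. It removes the definition bias but not clustering by centre, which needs separate handling.

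### The between-group chi-square, Mann-Whitney and Kruskal-Wallis tests ignore centre, so their 0.05 level is not assured and is too lenient where the compared groups differ between centres

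*Combined protocol and SAP*

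**What the plan says.** The Statistical analysis section prescribes the tests for categorical and continuous data "between groups using the chi-square test, whereas continuous data were compared between groups using the ManneWhitney or KruskaleWallis test". No centre term, stratification or cluster adjustment is attached to them, and the groups are not named. One threshold covers everything: "All tests were two sided, and a p value less than 0.05 was considered to be significant".

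The section then turns to HbA1c: "A linear mixed-effect regression model was used to identify the predictors of HbA1c among clinically relevant variables". Here centre does enter: "The centre was included in the model as a random effect because participant outcomes were expected to differ from centre to centre". Nothing extends that adjustment to the other tests.

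On sampling, the Study Design section says data came from "questionnaires sent by e-mail to adult and paediatric diabetes care centres" and that eligible clinic attenders were enrolled consecutively. The text just before the Statistical analysis heading lists facts recorded per centre: "Information about the organisation of each centre included the number of people with T1DM", followed by the start of CSII treatment, team composition and round-the-clock availability.

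**The concern.** The plan states that participants in the same centre resemble one another, then applies tests that assume they do not. For HbA1c there is a centre-aware model. For severe hypoglycaemia, ketoacidosis, emergency visits, complications and lipids there is none, so any significance claim rests on the pooled tests.

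Whether this matters for a given comparison depends on how the groups fall across centres:

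- **Adult versus paediatric** is the clearest candidate, because participants come through adult and paediatric centres.
- **Centre organisation** is affected if it is tested with participants as the unit.
- **Device type or sensor use** is affected if it varies by centre.

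Consecutive enrolment does nothing to balance groups within centres. In these comparisons, ordinary variation between centres can pass p<0.05 and be read as a difference between groups. Because the groups are undefined, a reader cannot tell these p values from the ones that hold their level.

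**Working it through.** **Inputs from the documents.** The three tests, two-sided 0.05, and the stated expectation that outcomes differ by centre (ICC above zero). The plan gives no sample size, power, number of centres, centre size or ICC, so it has no derived figure to reproduce.

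**Assumed inputs.** m = 10, 20 or 50 participants per centre; outcome ICC (ICC_y) = 0.01, 0.05 or 0.10; 60 equal centres in the simulations. ICC_x is the within-centre correlation of group membership: 1 if whole centres fall in one group, 0 if membership is unrelated to centre.

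**Formula, two groups.**

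DE = 1 + (m − 1) × ICC_y × ICC_x

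Actual level = 2 × [1 − Φ(1.96/√DE)]

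With ICC_y = 0, DE = 1 and the level is 0.05, as it should be.

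**Groups fixed by centre (ICC_x = 1).** For example, at m = 20 and ICC_y = 0.05, DE = 1 + 19 × 0.05 = 1.95, 1.96/√1.95 = 1.40, and the level is 0.160.

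| m | ICC_y 0.01 | ICC_y 0.05 | ICC_y 0.10 |
|---|---|---|---|
| 10 | 0.060 (DE 1.09) | 0.104 (DE 1.45) | 0.155 (DE 1.90) |
| 20 | 0.072 (DE 1.19) | 0.160 (DE 1.95) | 0.250 (DE 2.90) |
| 50 | 0.108 (DE 1.49) | 0.291 (DE 3.45) | 0.420 (DE 5.90) |

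**Three groups fixed by centre.** Kruskal-Wallis has 2 degrees of freedom and critical value 5.99, so the level is exp(−5.99/(2 × DE)). This gives exp(−2.75) = 0.064 at DE 1.09, exp(−1.54) = 0.215 at DE 1.95 and exp(−0.51) = 0.60 at DE 5.90.

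**Group mix varying by centre, not fixed by it.** The lower end is m = 10, ICC_y = 0.01; the upper end is m = 50, ICC_y = 0.10.

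- ICC_x = 0.3: DE = 1 + 9 × 0.01 × 0.3 = 1.027 to 1 + 49 × 0.10 × 0.3 = 2.47; level 0.053 to 0.212.
- ICC_x = 0.1: DE = 1.009 to 1.49; level 0.051 to 0.108.

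**Simulation of the tests themselves** (60 centres, same grid, 2000 replicates per cell, binary outcome with prevalence 0.30). Each entry is the range over the grid.

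| Group structure | Mann-Whitney | Kruskal-Wallis, 3 groups | Chi-square |
|---|---|---|---|
| Fixed by centre | 0.065 to 0.413 | 0.066 to 0.596 | 0.061 to 0.406 |
| ICC_x = 0.3 | 0.047 to 0.199 | 0.054 to 0.295 | 0.049 to 0.203 |
| ICC_x = 0.1 | 0.048 to 0.108 | 0.054 to 0.122 | 0.047 to 0.121 |

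With group unrelated to centre, all three tests gave 0.039 to 0.056. With groups balanced within centres they gave 0.031 to 0.054, which is slightly conservative at higher ICC.

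At m = 20 and ICC_y = 0.05 with groups fixed by centre, the grid gave 0.158, 0.203 and 0.157. Separate runs gave 0.155 to 0.167 for Mann-Whitney and 0.215 to 0.216 for Kruskal-Wallis. The chi-square result depends on the scale of the ICC: 0.147 to 0.172 on the observed binary scale, and 0.103 to 0.119 on a latent scale that is then dichotomised. At m = 50 and ICC 0.10 the corresponding figures were 0.44 and 0.31. All exceed 0.05.

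**Does a remedy restore the level?** On the same grid, rank regression with cluster-robust errors gave 0.048 to 0.057 for groups fixed by centre. For an exposure with ICC_x = 0.3 and its centre mean added, it gave 0.046 to 0.059.

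**The case against.** The plan never says which groups are compared. The affected comparisons are inferred from the variables collected; contrasts such as gender may sit where the tests hold their level. Centre organisation may be compared with one record per centre, in which case no clustering arises. The only inferential aim spelled out is to find predictors of HbA1c, and that model includes centre. The pooled tests follow directly on the median and IQR description and could be read as descriptive, with no primary endpoint resting on them. Every input to the size is assumed, the highest figures come from one extreme corner, and the chi-square figures depend on the ICC scale.

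Much of this stands, and it limits the point. The inflation is conditional, its size is unknown, and the missing group definitions are part of the fault. It does not remove the point. The plan does not label the tests descriptive; it applies the 0.05 rule to all of them. The direction needs no assumed figure: a positive outcome ICC, which the plan itself expects, together with groups that differ between centres makes DE exceed 1.

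**Conclusion.** The concern holds, and it should be fixed. The plan expects "participant outcomes were expected to differ from centre to centre" to be true but leaves it out of every between-group test. Under the assumed 10 to 50 participants per centre and outcome ICC of 0.01 to 0.10, two-group tests have an actual level of 6% to 42% when groups are fixed by centre. At group-membership ICC 0.3 the level is 5.3% to 21%, and at 0.1 it is 5.1% to 11%. It stays near or below 5% when group is unrelated to centre or balanced within centres, so the tests are not lenient in general. The mechanism is certain; confidence in the size is only moderate, because no design figure is given. The HbA1c mixed model is not affected.

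**What to change.** 1. Define the groups to be compared and the outcomes tested in each comparison.
2. Wherever a p value is read against 0.05, use a centre-aware analysis: a linear mixed model on ranks or the log scale for continuous data, a logistic mixed model or GEE with cluster-robust errors for categorical data, and a count mixed model for event counts. Only rank regression with cluster-robust errors was checked by simulation here.
3. Where centre-level confounding of a participant-level exposure is a concern, add the centre mean of that exposure. A random intercept alone does not remove such confounding.
4. Analyse centre attributes, such as team composition and availability, with centre as the unit or with cluster-robust errors.
5. Report unadjusted chi-square and rank tests as descriptive, without significance claims.

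The cost is a few lines of SAP text and slightly more R code. No new data are needed, because the HbA1c model already requires the centre identifier. Some p values will become less favourable, and cluster-robust errors need a small-sample correction if there are few centres.

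### Only HbA1c has a covariate- and centre-adjusted model, so any between-group comparison of complications or acute events may reflect age, diabetes duration or centre

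*Combined protocol and SAP*

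**What the plan says.** The study design section describes an observational survey: "In this multicentre cross-sectional study, data were collected using questionnaires sent by e-mail to adult and paediatric diabetes care centres". It lists hypertension and "chronic diabetic complications (i.e. retinopathy, nephropathy and vasculopathy [cerebral, cardiac and peripheral]) was derived from local clinical management systems". The text that follows adds three acute outcomes for the preceding period. Severe hypoglycaemia is reported by participants, and "the frequency of episodes was expressed as the cumulative number of SH episodes per participant". Ketoacidosis and emergency visits are counted from medical records.

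The statistical analysis section then offers two kinds of method:

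- Crude tests. Categorical data are compared "between groups using the chi-square test, whereas continuous data were compared between groups using the ManneWhitney or KruskaleWallis test". The threshold is common to all: "All tests were two sided, and a p value less than 0.05 was considered to be significant".
- One regression: "A linear mixed-effect regression model was used to identify the predictors of HbA1c among clinically relevant variables". Its candidate variables are "age, duration of diabetes, duration of CSII treatment, type of device, use of sensor-based treatment, CHO counting and use of advanced pump functions", and centre enters as a random effect.

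No logistic, count, stratified or otherwise adjusted analysis is given for any outcome other than HbA1c. The section does not define the groups for the crude tests, does not say which variables are compared, and does not call those tests descriptive.

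**The concern.** Nobody was randomised to a device or to sensor use, and the sample runs from children to adults. Chronic complications can be expected to accumulate with age and years of diabetes. A group that is older or longer diagnosed may then show more of them with no contribution from the grouping variable, and a crude test cannot tell the two apart.

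The plan already accepts this logic for HbA1c. It treats age and diabetes duration as clinically relevant there, and its reason for the centre effect is that outcomes in general are expected to vary by centre. The same reasoning covers the other outcomes, but the adjustment is not carried over to them. The crude tests also treat participants from one centre as independent.

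At stake is the reading of any p value below 0.05 for a complication or acute event. Enrolling more people does not help: the bias stays the same while the test becomes more likely to declare it significant.

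**Working it through.** **Step 1: match outcomes to methods.**

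| Outcome | Adjusted for age, duration, centre? | Other stated method |
|---|---|---|
| HbA1c | Yes, linear mixed model | Rank tests |
| Hypertension, retinopathy, nephropathy, three vasculopathies | No | Chi-square |
| Severe hypoglycaemia, ketoacidosis, emergency visits | No | None assigned by name; rank tests on counts, or chi-square on any/none, are what is available |

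**Step 2: is there a figure in the plan to reproduce?** No. The documents state no sample size, prevalence, group size or duration difference. What follows is illustration, and every input except the two-sided 0.05 level is an assumption.

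**Step 3: a difference in mean duration.** Assume no true group effect, reference prevalence p0, a log-odds slope b of 0.05 to 0.08 per year of diabetes (odds up about 5-8% a year), a duration gap of d years, and n per group.

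- Crude OR = exp(b × d)
- p1 = odds1 / (1 + odds1), where odds1 = [p0 / (1 − p0)] × OR
- Rejection probability ≈ 1 − Φ[(1.96 × SE0 − (p1 − p0)) / SE1], with SE0 pooled and SE1 unpooled (the opposite tail is added; it matters only for very small differences)

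For p0 = 0.20, d = 5, n = 500:

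- b = 0.05: OR = exp(0.25) = 1.28; p1 = 0.243; difference 0.043; SE0 = 0.0263, SE1 = 0.0262; rejection 37%.
- b = 0.08: OR = exp(0.40) = 1.49; p1 = 0.272; difference 0.072; SE0 = 0.0269, SE1 = 0.0268; rejection 76%.

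The same formula with other inputs:

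| p0 | Gap (years) | n per group | Rejection (nominal 5%) |
|---|---|---|---|
| 20% | 5 | 500 | 37-76% |
| 20% | 5 | 250 | 21-47% |
| 20% | 3 | 250 and 500 | 11-35% |
| 20% | 1 | 500 | 6-8% |
| 5% | 5 | 500 | 15-32% |

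The formula treats everyone in a group as having the same duration. Allowing an assumed within-group SD of 10 years (20% prevalence, 5-year gap, 500 per group) gives a crude OR of 1.27-1.43 and rejection of 35-67%, somewhat lower.

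**Step 4: a different set-up.** Take two duration strata with risk 10% at short duration and 20-40% at long duration, no group effect within either stratum, and 500 per group. With long-duration shares of 40% and 60%, the crude risks are 0.6 × 0.10 + 0.4 × 0.20 = 0.14 and 0.4 × 0.10 + 0.6 × 0.20 = 0.16 at the low end (OR 1.17), and 0.22 and 0.28 at the high end (OR 1.38). Rejection is 14-59%. Shares of 45% and 55% give 7-20%, and 30% and 70% give 43-99%. Equal shares give the nominal 5%.

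**Step 5: what was not computed.** No figure was derived for severe hypoglycaemia, ketoacidosis or emergency visits, nor for clustering. For these the point rests on the absence of an adjusted method, not on a demonstrated size or direction of bias.

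**The case against.** A reader might infer that complications and acute events definitely are compared by device, sensor use or age group, and that the differences will be reported as group effects. The documents do not go that far. They name neither the groups nor the compared variables, and they do not say how a crude difference would be interpreted. Complications appear beside demographics and routine laboratory values, the only regression aim stated is HbA1c, and crude tests are ordinary for describing a survey sample. This stands: the bias is conditional on groups that differ in age, duration or centre, and on p values being used for more than description. It does not remove the gap, because the plan sets a significance threshold and never limits the crude tests to description.

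Four objections to adjustment also stand in part.

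- An adult-versus-paediatric contrast is in essence defined by age, so an age-adjusted effect for it would be extrapolation.
- Severe hypoglycaemia has one definition for adults and another for children. No covariate repairs that.
- Complications are recorded as present, with no onset date mentioned. One may predate CSII or have influenced the choice of device, so adjusted estimates remain associations.
- Modelling all nine outcomes would raise multiplicity. The crude tests already carry that problem, and modelling only the comparisons that support a conclusion limits it.

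Finally, the illustration is sensitive to its inputs. A 1-year gap leaves rejection close to nominal, and the documents do not say which case applies.

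**Conclusion.** The point holds in conditional form. It is certain from the text that only HbA1c has a covariate- and centre-adjusted model, and that crude tests at p<0.05 are the only methods available for the other outcomes. It follows that a between-group difference in those outcomes may be due to age, diabetes duration or centre, and that the plan has no analysis to separate these. That it will be, or that any particular comparison is misleading, does not follow.

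The possible size runs from negligible (6-8% rejection for a 1-year gap) to serious (37-76% for a 5-year gap), both at 20% prevalence and 500 per group. These values rest wholly on assumed prevalence, slope, gap and group size, and apply to chronic complications only. The HbA1c model is not called into question. This is an inexpensive improvement worth making.

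**What to change.** - Name the groups and the variables to be compared, and label the crude tests descriptive.
- For any device or sensor comparison of these outcomes on which a conclusion rests, fit a mixed model with centre as random effect and with age, diabetes duration and the grouping variable as fixed effects: logistic for each complication and for any ketoacidosis, count or any/none for emergency visits and severe hypoglycaemia. Report adjusted odds ratios or rate ratios with 95% confidence intervals.
- Analyse severe hypoglycaemia separately in adults and children.
- Do not age-adjust an adult-versus-paediatric contrast; leave it descriptive.
- For rare outcomes, use few covariates or a penalised fit.
- Report the results as cross-sectional associations, not as effects of the device.

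Age, diabetes duration and centre are already available, so no new data are needed, and the models can be run as a re-analysis if the first analysis is complete. The cost is extra analysis work and wider intervals for rare outcomes.

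### The HbA1c mixed model omits gender and type of diabetes, although both are collected and entry is not limited to type 1; listed coefficients may be partly confounded, possibly negligibly

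*Combined protocol and SAP*

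**What the plan says.** All references are to the combined protocol and SAP.

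- **Purpose of the model** (Statistical analysis): "A linear mixed-effect regression model was used to identify the predictors of HbA1c among clinically relevant variables".
- **Predictors** (same sentence, introduced by *i.e.*): "age, duration of diabetes, duration of CSII treatment, type of device, use of sensor-based treatment, CHO counting and use of advanced pump functions".
- **Centre** (Statistical analysis): "The centre was included in the model as a random effect". The reason given is that outcomes may vary because the centres themselves differ, rather than because different participants attend them.
- **Variables collected** (Study Design): "demographic data (i.e. age, gender, type of diabetes, duration of diabetes, duration of treatment with CSII and body mass index", among others.
- **Entry** (Study Design): "Subjects treated with CSII for at least 1 year were consecutively enrolled". Exclusions: "Exclusion criteria were previous diagnosis of dementia or psychosis and pregnancy in progress".
- **Only mention of type 1** (end of Study Design): "Information about the organisation of each centre included the number of people with T1DM". This describes centres and is not a condition for enrolling participants.

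The plan gives no reason for leaving gender or type of diabetes out of the model. It states no sample size, no HbA1c standard deviation and no expected mix by type or gender.

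**The concern.** The study is cross-sectional, and nobody is randomised to a sensor, a device or carbohydrate counting. In such data the regression model is the only adjustment, and its coefficients will naturally be read as adjusted associations.

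Two things are at stake. First, a model meant to find predictors of HbA1c cannot find one that is never entered. That holds whether or not there is any confounding. Second, suppose sensor users and non-users of similar age, disease duration and so on, within the same centre, still differ in gender or type of diabetes, and HbA1c differs by that characteristic. The sensor coefficient then carries part of the difference. The same applies to carbohydrate counting, device type and advanced functions.

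**Working it through.** **1. Collected items against model terms**

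| Demographic item collected | In the HbA1c model? |
|---|---|
| Age | yes |
| Gender | no |
| Type of diabetes | no |
| Duration of diabetes | yes |
| Duration of CSII | yes |
| Body mass index | no |

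Three of the six demographic items are in the model. The other four listed predictors are device type, sensor use, carbohydrate counting and advanced functions (3 + 4 = 7). Neither gender nor type appears.

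**2. Could type vary in the sample?** The entry rule is at least one year of CSII, and the exclusions concern dementia, psychosis and pregnancy. Type is itself a recorded variable. Nothing makes it constant by design, and the actual mix is not given.

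**3. Does the centre effect cover the gap?** Only in part. A random intercept takes up some of the difference in mix between centres. It is the same for everyone in a centre, so it cannot adjust for gender or type among that centre's participants. The plan's own contrast between centres and the people who attend them needs participant characteristics in the model if the two are to be separated.

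**4. Size.** The plan has no figure to reproduce. As an illustration, for one omitted binary variable:

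shift in sensor coefficient ≈ γ × (p₁ − p₀)

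Here γ is the HbA1c difference by the omitted variable, and p₁ and p₀ are its shares in sensor users and non-users, all given the other covariates and centre. Every input is an assumption. HbA1c is taken in percentage points.

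| Omitted variable | γ | p₁ − p₀ (absolute) | Shift (absolute) |
|---|---|---|---|
| Type | 0 (or any) | any (or 0) | 0 |
| Type | 0.3 | 0.02 | 0.3 × 0.02 = 0.006 |
| Type | 0.5 | 0.10 | 0.5 × 0.10 = 0.05 |
| Gender | 0 (or any) | any (or 0) | 0 |
| Gender | 0.1 | 0.05 | 0.1 × 0.05 = 0.005 |
| Gender | 0.2 | 0.15 | 0.2 × 0.15 = 0.03 |

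If both act in the same direction, the largest of these gives 0.05 + 0.03 = 0.08. If they act in opposite directions, they partly cancel.

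**5. Check with a random centre intercept.** A simulation with assumed values (60 centres of 35 participants, 25% sensor users, centre SD 0.3, residual SD 0.9, 20 runs) compared the sensor coefficient without and with the two variables. Gender and type depended on the participant's own sensor use. Non-type-1 participants were fewer among sensor users, so the two shifts have opposite signs.

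- Mild (γ 0.1 for gender, 0.3 for type): formula 0.1 × 0.05 + 0.3 × (0.01 − 0.03) = −0.001; simulation −0.0007.
- Strong (γ 0.2 and 0.5): formula 0.2 × 0.15 + 0.5 × (0 − 0.10) = −0.02; simulation −0.017.
- No effect of either variable: formula 0; simulation 0.0006.

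Agreement is close for 20 runs. The centre intercept did not remove a shift that arises within centres. The simulated model left out the other six listed predictors, so it does not show how much of the effect of type age and diabetes duration would already capture.

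**The case against.** **The plan chose its candidate variables and breaks no promise.** It speaks of clinically relevant variables and nowhere undertakes to enter everything collected. This stands: there is no contradiction in the text. But the label does not explain why two recorded participant characteristics are left out.

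**No causal estimand is stated.** This also stands. The confounding point applies only where a coefficient is read as an adjusted association. That the model cannot identify gender or type as predictors does not depend on this reading.

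**The list may not be exhaustive.** Carbohydrate counting is a model term but appears in no list of collected data, so this short document does not itemise everything. The *i.e.* still makes a closed list the natural reading, though not a certain one.

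**Why these two?** Body mass index, hypertension, complications and self-monitoring frequency are also collected and unlisted. It is a judgement, but gender and type generally precede pump and sensor use, whereas the others may be consequences of glycaemic control or of treatment. Adding those is less clearly an improvement.

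**The sample may be almost all type 1.** The centre-level count of people with T1DM hints at such a focus, and age and diabetes duration may stand in for type. If so, the shift from type is close to zero. The documents do not settle it.

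**Stronger readings that a reader might infer.** One is that the sensor coefficient is materially biased. The documents give neither the link with HbA1c nor the link with sensor use, so this is unsupported. Harsher assumptions raise the figure (0.8 × 0.13 = 0.104), but that reflects the chosen inputs and says nothing about this study. Another is that age is mis-modelled as a straight line. The plan does not say how age enters, and a linear mixed model is linear in its parameters and can hold curved terms.

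**Conclusion.** The omission is clear from the text: gender and type of diabetes are collected, type is not fixed by the entry criteria, and neither is among the seven listed predictors. The model as written cannot identify them as predictors of HbA1c. Any listed coefficient read as an adjusted association is partly confounded if gender or type is related both to HbA1c and to that predictor, given the other covariates and centre.

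The size cannot be estimated from the documents. The illustrative range above starts at zero and rests wholly on assumed HbA1c differences and imbalances. This is an improvement worth considering, not a demonstrated error in a result.

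**What to change.** In the main HbA1c model, add gender and type of diabetes as fixed effects alongside the seven listed predictors and the random centre effect. If either is left out on purpose, state the reason.

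A fit restricted to type 1 should be a sensitivity analysis at most. As the main analysis it would change the population to which the results apply.

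The cost is about two degrees of freedom: one for gender and one for a two-level type variable, with more if type has more than two levels. No new data are needed. Because the section is written in the past tense, the change may mean refitting the model as well as amending the text.
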